5.3.2 The Informed Consent process for participants with limited literacy

If you are enrolling participants who cannot read the consent materials due to limited literacy skills:

- It is recommended that an impartial witness observe the consent process.
 - In the food pantry setting, impartial witnesses could include: other study staff or volunteers, food bank / pantry staff or volunteers, or host site staff / volunteers.
- Consent materials should be presented orally, including the HIPAA form (see next section)
- Sufficient time should be allowed for questions to be asked and answered, both by the participant and by the person obtaining consent, to ensure the subject comprehends the consent information.
- **Review eligibility:** Before initiating the informed consent process, be sure to review the eligibility of the potential participant and make sure this information is accurately recorded on the screening checklist.
- **Verbally explain the study and research activities:** Using the informed consent form as a guide, verbally go through each section (section headings are in bold) of the form with the potential participant, speaking clearly and allowing the potential participant to ask questions. The consent form and consent process must be completed in the potential participant's preferred language (either English or Spanish).

- **Assess client comprehension:** In addition to fielding questions from the potential participant, the person obtaining the consent must assess the food bank client's comprehension by using the teach-back method whereby the person obtaining consent asks open-ended and non-directive questions that require the potential participant to explain in his or her own words the basic study procedures. Research staff should make sure the potential participant can describe why the research is happening, what is being asked of him or her, and the risks and/or benefits to taking part in the study. Some sample questions include:
 - If someone in your family asked you what this study was about, what would you tell them?
 - How often might you need to pick up food boxes as part of this study?
 - Where will you be picking up your food boxes during the study?
 - If you had a question or problem during the study, who could you contact?
 - What else might you receive for participating in this study?
 - How many diabetes classes might you be expected to participate in during the study?
- **Obtain consent:** Once all questions are answered by both parties and the individual has agreed to participate in the study, the participant should sign and date the consent form where indicated. To document the consent process, Western Institutional Review Board's recommendations are consistent with guidance endorsed by the FDA (FDA 21 CFR 50.25). If the participant verbally agrees to participate in the study:
 - If capable of doing so, the participant signs or marks an X to signify consent.
 - The witness signs and personally dates the consent form. By doing so the witness attests that the consent information was accurately explained and that the participant apparently understood the information, and informed consent was given freely.
 - The research staff that performed the consent procedures should sign and date the same consent form. The participant, witness, and research staff should also sign a second consent form for the participant to keep as a copy for their records.

Important notes: It is the responsibility of the research staff obtaining consent to judge the participant's comprehension of the consent information including the understanding that participation is voluntary and that the participant has the right to withdraw at any time during the study. If any study staff doubts the participant's consent comprehension, he/she should not enroll the individual in the study.

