2.5 Study Sites

Sites participating in FAITH-DM include: Alameda County Community Food Bank (ACCFB), Gleaners Community Food Bank of Southeastern Michigan (GCFB), and the Houston Food Bank (HFB)

The roles and responsibilities of the food banks include:

- Maintenance of study binder with updated MOP
- Participation in protocol finalization and preparation of study materials
- Compliance with protocol, MOP, IRBs (UCSF Committee on Human Research, Western IRB, Urban Institute IRB) and Federal and state regulations
- Accountability for administration of study intervention
- CITI certification (as necessary)

- Membership in Steering Committee
- Recruitment, screening, enrollment, and follow-up/retention of participants
- Protection of participants' rights
- Data collection from enrollment through study completion, including: survey data, HbA1c, and health care utilization data (requiring medical chart abstraction)
- Transfer of data to Coordinating Center and resolution of all queries
- Communication of questions, concerns, and/or observations to the Coordinating Center (FANO, [name])
- Development and maintenance of MOUs with collaborating health care sites
- Communication with primary care providers
- Development of expertise in administration of all intervention components, including diabetes education
- Maintenance and quality control of point-of-care HbA1c machines and glucometers, including CLIA Certification and other regulatory requirements (as necessary)
- Assembly and distribution of food packages
- Communication and reporting per project guidelines and timeframes with FANO and UCSF staff (e.g., progress reports, budget reports, food box content reports, etc.)

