5.3 Informed Consent

Informed consent is a process in which an eligible individual is informed of all aspects of the research that are relevant to his or her decision and is then given the chance to choose whether or not to participate without any consequence to usual care.

US regulations 21 CFR 50 and 45 CFR 46 require that informed consent be documented by the use of an informed consent form approved by the responsible institutional review board (IRB) and signed and dated by the participant and research staff at the time of consent. Detailed instructions for obtaining informed consent are listed below and a quick guide to the informed consent process (Western Institutional Review Board, except from “A Guide for Researchers”) can be found in **Appendix T**. In addition, a copy of this study’s informed consent form can be found in **Appendix AE**.

The informed consent form and process has been approved by the Western Institutional Review Board.

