- Consider the **subject's reading abilities**. Check to make sure the protocol does not exclude subjects unable to read. If enrollment of limited or nonreaders is allowed, involve an impartial witness in the informed consent process. WIRB has posted a standard generic form you can use to document the involvement of an impartial witness if your approved consent form lacks the necessary signature block for that; see the Download Forms page of www.wirb.com for the document titled "[Impartial Witness form for Limited and Non-Readers.](#)"
- **Answer all questions.**
- To the extent possible, make sure the subject **understands enough information** about the research study to give informed consent.
- To the extent possible, make sure the subject can consent **free from coercion or other undue influence**.
- Since the informed consent process continues throughout the subject's participation in the study, **consent should be informally verified on a continuing basis**.
- **Significant new information** must be given to the subject, and continuing consent documented in some way; for example, new risk information presented to the subject in an addendum to be signed by subjects who agree to continue to participate.

E. Issues to consider during the consent process

- Was the subject alert and, in your opinion, able to read and understand the language in the consent form?
- If the subject was unable to read the consent form, and limited or non-readers were allowed to participate, did you have an impartial witness present for the

entire process? (An impartial witness is someone with adequate reading ability who is independent of the trial, who cannot be unfairly influenced by people involved in the trial, who attends the informed consent process while the consent form is being read to the subject, who reads the informed consent form and any other written information supplied to the subject, and who is willing to attest to this by signing the consent form.)

- If the subject is not fluent in English, was an approved translation of the consent form provided in the primary language of the subject? Was there also a bilingual translator present to assist with the informed consent process? Note: a translator alone is not considered adequate.
- Was the subject under any pressure (for example, family pressure, lack of medical insurance) to participate in the research? Was this discussed?

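### Section 5.3.2 accepts study staff as the impartial witness for people who cannot read the consent form and only recommends a witness, which conflicts with Appendix T and with its own signature step

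*Combined protocol and SAP*

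**What the plan says.** Section 5.3.2 sets out consent for people who cannot read the materials because of limited literacy. Its opening item reads "It is recommended that an impartial witness observe the consent process". It then states that "impartial witnesses could include: other study staff or volunteers, food bank / pantry staff or volunteers", and adds host-site staff and volunteers as a third group. Later in the same section, under documentation of consent, the wording is unconditional: "The witness signs and personally dates the consent form". By signing, the witness attests that the information was explained accurately, that the participant appeared to understand it, and that consent was free. The witness also signs the copy that the participant keeps.

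Section 5.3 refers the reader to Appendix T as "a quick guide to the informed consent process". Under investigator responsibilities, Appendix T instructs: "If enrollment of limited or nonreaders is allowed, involve an impartial witness in the informed consent process". Its list of issues to consider asks whether such a witness was there throughout, and defines the role: "An impartial witness is someone with adequate reading ability who is independent of the trial". The definition goes on to require that the person not be open to unfair influence from those involved in the trial.

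Section 2.5 gives the food banks, as study sites, responsibility for "Recruitment, screening, enrollment, and follow-up/retention of participants".

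**The concern.** In this consent path the witness is the one check meant to come from outside the study team. Teach-back and the rule against enrolling someone whose understanding is in doubt are both applied by study personnel. If another study team member serves as witness, all the safeguards sit with the people running the trial.

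The path is likely to be used. Section 3.4 tailors education to literacy level, section 3.4.3 supplies a guide written for low-literacy readers, and section 5.4.1 sends HIPAA authorization for limited readers through the same steps. Participants also depend on these organizations for food. Section 5.5 recognizes that pressure when it warns staff not to imply that food depends on signing the medical records release.

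There is a practical side as well. Section 14.2 has monitors verify that consent was obtained and documented, and Appendix F codes a consent form lacking a required signature as a deviation. While the witness is recommended in one place and signs without condition in another, a monitor cannot tell whether a missing witness signature is a deviation.

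**Working it through.** No arithmetic applies: the point involves no sample size, error rate or power. The check is a comparison of the current text of section 5.3.2, section 5.3, Appendix T and section 2.5.

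1. **Who may witness.** Section 5.3.2 lists three groups: study staff or volunteers, food bank or pantry staff or volunteers, and host-site staff or volunteers. Appendix T sets two tests: independence from the trial, and freedom from unfair influence by those involved in it.
   - Study staff and study volunteers fail the first test by definition.
   - Food bank personnel are doubtful on both. The food banks are the study sites and carry out enrollment (section 2.5). Section 8 has the research assistant at each food bank enroll participants, and Appendix AY lists research assistants and project managers under the food banks. A food bank colleague with no FAITH-DM role still works for the organization running the trial locally.
   - Pantry personnel may be more distant, but the manual also gives them trial tasks: pantry staff take part in the one-on-one education in section 3.4.2.
   - Host-site personnel, such as those of a church or community center that houses a distribution, are the group on the existing list with the least connection to the trial.

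2. **Whether a witness is needed.** Three statements have to be read together.
   - Section 5.3.2, opening item: recommended.
   - Section 5.3.2, documentation step: the witness signs, dates and attests, with no condition.
   - Appendix T, investigator responsibilities: involve one if limited readers or nonreaders may be enrolled. They may be, since section 5.3.2 exists for that purpose.

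   Two of the three treat the witness as a fixed part of the process. The opening item is the outlier.

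3. **Result.** Two conflicts are confirmed in current text. A site following the list in 5.3.2 can use a witness who fails the manual's own definition, and 5.3.2 is inconsistent on whether the witness is optional.

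4. **Size.** The documents give the overall recruitment goal (720) but no share of participants expected to have limited literacy. The number who would consent this way cannot be derived.

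**The case against.** The best case on the other side has four parts.

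- **Standing of Appendix T.** Section 5.3 describes the numbered subsections as the detailed instructions and the appendix as a short guide. The appendix is adapted from the IRB's general guide for researchers and carries material that does not fit this trial, such as consent by legally authorized representatives. On that view, trial-specific text simply departs from generic advice. This has some force on precedence. However, the manual adopts the appendix by reference, and it is the only place where the term impartial witness is defined. Section 5.3.2 uses the term without offering another definition.

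- **The process was approved.** Section 5.3 says that the IRB approved the consent form and process. This stands as a limit on the consequences, but approval does not tell a site which of two conflicting instructions to follow.

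- **A witness would be present anyway.** A reader might infer from the word recommended that a site following 5.3.2 could document consent with no witness at all. The section as a whole does not support that: its documentation step assumes a witness who signs. What remains is an internal inconsistency. The checklist in Appendix T does qualify the witness signature as applying where required, but that is a general item, and the text specific to limited readers has the witness attest by signing.

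- **No harm is shown.** A reader might go further and infer that the consent of limited-literacy participants would not stand, or that their HbA1c data could be lost after randomization. The documents do not support either. The process was approved, teach-back is required, and staff who doubt comprehension must not enroll. Section 9.4 keeps participants in follow-up unless they withdraw consent, section 13.4.4 plans an intent-to-treat estimate, and no section removes anyone from analysis for a witness defect. This part of the objection stands in full.

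The consent form itself (Appendix AE) is not reproduced in the text available, so whether it has a witness line is unknown. Appendix T anticipates this by pointing to a separate IRB form for forms without one.

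**Conclusion.** The point holds as a contradiction in consent procedure. Section 5.3.2 names as acceptable a category of witness that the manual's own definition rules out, and it is inconsistent, internally and with Appendix T, on whether a witness is mandatory. The first is a wrong rule rather than a missing detail, because a site that follows it exactly obtains a witness who is not independent.

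Its weight comes from participant protection. It changes no estimand, sample size or analysis. The conclusion assumes only that the independence description in Appendix T is meant to apply to this trial, which the cross-reference in section 5.3 supports. The case for a wording change is strong because the remedy is cheap and the people concerned are the least able to check the form for themselves.

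**What to change.** Reconcile the two parts of section 5.3.2 with Appendix T:

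1. State in 5.3.2 that a witness is required, not recommended, for any participant who cannot read the consent form.
2. Delete study staff and study volunteers from the list of acceptable witnesses.
3. Limit witnesses to people with no FAITH-DM role. Name host-site staff or volunteers as the preferred choice, and allow food bank or pantry personnel only if the IRB confirms that it regards them as independent of the trial.
4. Review limited-literacy consents already signed, identify who witnessed each, and ask the IRB whether any witnessed by study staff need action. This is a question for the IRB, not a presumption that those consents are defective.

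The cost is a few wording changes, one question to the IRB and a check of stored forms. The operational downside is that an uninvolved witness must be available at the enrollment visit, which may occasionally delay an enrollment. Section 4.2 already provides for rescheduling within 2 weeks when enrollment cannot be completed in one encounter for lack of time, and the same arrangement could serve here. Host-site personnel are already on the manual's list, so no new category of witness is needed, although the documents do not show that one would be present at every distribution.

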5.3.3 Participant update process at T6

The IRB-approved consent forms include information on possible T12 activities that could occur in the event ancillary funding is obtained for the study. As a result of receiving this funding (**see section 17.3**) the MOP has been revised to reflect changes to study activities at T12. Western IRB approved of these changes and the updated research protocol on: 3/18/2016.

While these changes did not require a revision to original and existing informed consent processes, study staff will need to inform current and future study participants of all study activities and timelines accordingly:

- Use revised participant recruitment flyer and other materials to describe all participant activities and study timelines
- Verbally communicate all participant activities and study timelines when promoting study and recruiting participants
- Verify all participant activities and study timelines when completing informed consent process during participant enrollment (“If you are in the intervention group, we may contact you to perform HbA1c testing and follow-up 12 months after you enroll.”)
- Disseminate informational sheet (“Participant FAITH-DM Study Update”, **Appendix AW**) to all study participants at their 6-month marks (in-person and/or via mailings)

5.4 HIPAA Authorization

The Health Insurance Portability and Accountability Act authorization form is a separate document from the informed consent, and must be reviewed and signed by the study participant at the time of consent. The HIPAA authorization form is an extension of the informed consent form that pertains to the study purpose and procedures. When signed, this document authorizes the release of specified personal identifiable health information for use in this study and allows communication with a participant’s health care provider. The signed HIPAA authorization form must be faxed or securely sent to the health care provider before they can release any information about the patient.

5.4.1 Process for obtaining HIPAA authorization

The process for reviewing the HIPAA document and obtaining participant authorization is similar to the process for obtaining informed consent. It is usually easiest to append this document to the end of the informed consent form in order to review them in a single session with the potential participant. For this study, personal identifiable health information will be collected in the form of selected data from medical records.

We will collect information on healthcare use by each participant. Because part of the intervention involves a referral to primary care, we will also assess if an appointment with a primary care provider was made and kept. Furthermore, we seek to collect information on other health care utilization, including emergency department visits, hospitalizations, and primary care visits.

As with the informed consent, verbally discuss pages 6-7 of the HIPAA form, allow time for questions and review, employ the teach-back method, and if the participant agrees, obtain his/her signature. If the subject has limited literacy skills, refer to **section 5.3.2**.

Completed HIPAA documents should be kept with the associated informed consent documents in the secure site-specific binder. Again, documentation that HIPAA authorization was or was not provided should be made in the MS Access database. The HIPAA form can be found in **Appendix X**.

5.5 Medical Records Release Form

The Medical Records Release Form (**Appendix AO**) should be completed at the same time as the informed consent form and the HIPAA authorization form during participant enrollment. This form needs to be completed and signed by the participant in order to access clinic medical records as part of the Health Care Utilization Analysis. While the informed consent and HIPAA authorization forms are mandatory for participants, the medical records release form is optional. If a participant refuses to sign this form, they can still participate in the study, but we cannot request any of the participant's medical records from their provider. However, because the HCUA is an important part of this study, study staff should provide support and encouragement to participants to ensure they understand the form and request, and complete it as part of the enrollment process. Encouragement entails not only explaining the benefits of the information obtained in the study, but also emphasizing that the decision to sign the medical release form in no way impacts a person's participation in the study. **As such, encouragement excludes any action or statement that can be interpreted as coercive to the participant.** Coercive actions include, but are not limited to, putting undue pressure on the participant or implying that the participant will not receive FAITH-DM food boxes and/or any applicable intervention components, or regular food bank services if he or she does not sign the release form. Study staff should document in the MS Access database whether or not the medical records request form was completed for each participant.

When filling in the dates of requested information on the bottom of the first page of the Medical Release Form, please fill in the following dates specified in the "From" and "To" blanks.

- From: The date **6 months prior** to the day of enrollment of the participant
- To: The date the participant will have been in the study for **1 year from the day of enrollment**

Prior to asking the participant to sign the Medical Release Form, please **mark all fields** under "Specific type of information to be disclosed" with a check or X mark (with the exception of the "other" field, which you should leave blank).

6 Blinding and Unblinding (Masking and Unmasking)

This study is not blinded. However, to reduce bias in allocation, the randomization process will be completed by UCSF staff prior to enrollment of the first participant. The baseline survey should always be administered prior to determining the randomization status of the participant.

7 Study Measurements and Procedures

To ensure that assessments and measures are conducted consistently across study participants and sites, this section describes detailed procedures for:

- Universal precautions and safety
- Random blood glucose testing (including Quality Control testing)
- Point-of-care HbA1c testing (including Quality Control testing)
- Regulatory requirements for testing (CLIA certificates of waiver, medical waste permits and plans, licenses and certifications, county and/or state specific regulations, etc.)
- Survey administration
- Health care utilization plan

